#### B. Study sample and recruitment plan

Population: Adult males will be recruited from the Stratton VA Medical Center in Albany, NY. Recruitment will focus on individuals who have type 2 diabetes. Currently, there are over 5000 Veterans receiving care for type 2 diabetes at the Stratton VA Medical Center.

Potential subjects will be required to attend an individual information session and the requirements of participating in the study will be detailed along with the risks and benefits. At the information session, the requirements of the study, the time commitment, and risk and benefits will be described in detail. Following the session, interested subjects will be required to complete and sign a consent form and complete a study application. During this process, a study investigator will be available to answer all questions that may arise.

Subjects will be informed that participation is completely voluntary and they may withdraw from the study at any time. Should they choose to withdraw, they will be provided with a travel and meal stipend commensurate with the level of study that they have completed.

Interested volunteers will undergo a medical evaluation by a physician or nurse practitioner. The physician or nurse practitioner will review the volunteer's medical history, previous clinical laboratory tests, including a profile of hematological and biochemical parameters along with a hemoglobin A1C. The physician or nurse practitioner and research investigators will use the clinical screening and evaluation results to identify individuals who qualify for the study.

#### Inclusion Criteria:

- Male
- Ages 45 to 75 years at beginning of study
- BMI  $>25 \text{ kg/m}^2$
- HbA1C  $> 6.5$  and  $< 9$
- Medical diagnosis of type 2 diabetes for at least 6 months

#### Exclusion Criteria:

- Use of insulin
- Presence of chronic kidney disease (GFR  $\leq 45 \text{ mL/min}$ ), liver cirrhosis, gastrointestinal disease, pancreatic disease, or malabsorption syndromes
- Weight loss of  $>10\%$  of body weight over the last 6 months; routine participation in heavy exercise
- Heavy smokers ( $>20$  cigarettes per day)
- Unable or unwilling to give informed consent or communicate with study staff
- Other medical, psychiatric, or behavioral factors that in the judgment of the Principal Investigators may interfere with study participation or the ability to follow the intervention protocol
- Allergies to blueberries or blueberry products

#### D. Data analysis and sample size justification

Data analysis:

The data will be analyzed using a mixed model in order to partition variance from random and fixed effects. The model will account for age, BMI and the significance for other terms will be tested to determine if they are to remain in the model. Some terms may be used as covariates. Split-plot and split-split plot analysis will be used to partition variances from measurements for which there are repeated measures. Contrasts statements or appropriate multiple comparisons of means will be completed using least-square means.

Sample size:

Sixty males with type 2 diabetes will be recruited for the study. The sample size for this study is based on a standard deviation from a previous study conducted by Basu et al (13), which showed that 50 g of freeze-dried blueberry powder lowered systolic and diastolic blood pressure. A sample size calculation was estimated for a 1-factor ANOVA for a parallel-arm study with > 80% power to detect a significant difference. Twenty-four participants per group are needed, and 30 per group are determined based on a 20% drop out rate.

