### **4. METHODS:**

#### **A. Procedures**

**Treatment.** Participants will be randomly assigned to one of two treatment groups; either 1) 22 g of a control blueberry placebo treatment (matched in energy and carbohydrate content to the blueberry treatment; ingredients are maltodextrin, fructose, artificial blueberry flavoring and coloring, citric acid and silica dioxide) along with their free-living diet per day, 2) 22 g of a freeze-dried whole blueberry powder treatment along with their free-living diet per day. One cup of fresh blueberries is equivalent to approximately 22 g of freeze-dried whole blueberry powder. This amount was chosen as it is a reasonable amount of fruit for subjects with type 2 diabetes to consume. Subjects will be asked to consume 11 g of freeze dried blueberry powder or placebo, reconstituted with 240 ml water, with their morning and evening meals for 8 weeks. Participants will be counseled by a registered dietitian as to how the treatment is to be consumed, and compliance will be monitored by a daily questionnaire. In addition, the number of used and unused treatment packets will be tracked. Subjects will receive a 4 week supply of these products during a visit to the Stratton VA Medical Center. Treatments will be blinded to the study investigators and subjects (e.g., investigators and subjects will not know the composition of the treatments until after the study is complete). The US Highbush Blueberry Council will hold the code to the study treatments.

Subjects will be responsible for their own meals and will continue to follow their typical pattern of food intake (food consumption will be monitored periodically as described below).

**General Physiological Variables.** Body weight will be determined following an 8-h fast. Height will be measured with participants positioned in the Frankfort frontal plane. Each subject's height without shoes will be measured to the nearest 0.1 cm with a wall-mounted stadiometer. Waist and hip circumferences will be collected according to standard protocols. Body weight and composition, and waist/hip circumference will be obtained at baseline, at 4 weeks, then after 8 weeks of the study. These measurements require 30 minutes for the entire study.

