Blood pressure will be collected according to a standard protocol. Subjects will be taken to a quiet room with subdued lighting. The appropriate size cuff will be attached to the upper right arm according to the manufacturer's instructions. Blood pressure will be measured three times with a Dinamap Compact Blood Pressure Monitor, which will be programmed to take an initial reading and then a reading after 5 minutes and after 10 minutes. The arm will be adjusted so that the height of the upper arm is level with the heart. Subjects will have both feet flat on the floor. Subjects

will be instructed to refrain from consuming coffee for at least 30 minutes prior to the measurement and will be advised to empty their bladder prior to the measurement. Blood pressure will be obtained at baseline, at 4 weeks, then after 8 weeks of the study. Each measure requires 20 minutes (20 minutes x 3) = 1 hour for the entire study.

**Blood Collection.** Twice during the study, at baseline and after the 8-week treatment period, 25 ml of blood will be collected from the antecubital veins of subjects following an overnight fast. A total of 50 ml of blood will be collected. Plasma and serum will be collected then analyzed. Plasma and serum will be used for analysis of health indices and biomarkers of cardiovascular disease and diabetes (cardiometabolic parameters). Blood will be analyzed for a complete metabolic panel, blood lipids, lipoproteins and inflammation (triglycerides, total cholesterol, HDL cholesterol, LDL cholesterol, and high sensitivity CRP) along with markers of glucoregulatory mechanisms (hemoglobin A1C, fructosamine, insulin, and glucose). Each blood draw requires 20 minutes, (20 minutes x 3) = 1 hour for the entire study.

**Urine Collection.** Twice during the study, at baseline and after the 8-week treatment period subjects will provide a urine sample of at least 10 ml. Urine will be collected in plastic containers and will be stored on ice during collection and until samples can be delivered to the laboratory. Each urine collection requires 5 minutes, (5 minutes x 2) = 10 minutes for the entire study. Urine will be analyzed for urine microalbumin to creatinine ratio.

**Questionnaires.** Participants will be asked to complete a daily questionnaire regarding their general health; if they consumed any over the counter or prescription medications and their general feeling of well-being.

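### Section 4.D does not commit to adjusting for each outcome's baseline value and names no treatment contrast; fixing a baseline-adjusted week-8 difference needs no new data and usually gains precision

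*Combined protocol and SAP*

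**What the plan says.** Section 4.D (Data analysis and sample size justification) specifies a mixed model. Its rule on covariates is: "The model will account for age, BMI and the significance for other terms will be tested to determine if they are to remain". The sentence that follows leaves further adjustment open: "Some terms may be used as covariates". On repeated measurements it says "Split-plot and split-split plot analysis will be used to partition variances from measurements for which there are repeated measures", without saying whether baseline is a response level or a covariate. On the comparison itself it says "Contrasts statements or appropriate multiple comparisons of means will be completed using least-square means". It names no visit, and does not say whether the effect is a week-8 difference, a change from baseline, a treatment-by-time term or a treatment main effect.

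The sample size paragraph of the same section uses a simpler model: "A sample size calculation was estimated for a 1-factor ANOVA for a parallel-arm study".

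Section 4.A (Procedures) shows that baseline data exist for all these outcomes. For body measurements: "Body weight and composition, and waist/hip circumference will be obtained at baseline, at 4 weeks, then after 8 weeks of the study". For blood pressure: "Blood pressure will be obtained at baseline, at 4 weeks, then after 8 weeks of the study". Blood and urine are taken at baseline and after the 8-week treatment period.

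**The concern.** At least three analyses fit the wording: a week-8 difference adjusted for baseline, a change (treatment-by-time) contrast, and a week-8 comparison adjusted only for age and BMI. They use the baseline value differently and usually differ in precision. With about 24 completers per arm, a difference of several points of power is worth having when it needs no new data.

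The open wording also lets covariates and contrast be settled after results are seen, because terms stay or go by significance test and no contrast is fixed. That weakens the interpretation of whichever p-value is reported.

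**Working it through.** **The plan's own figures.** The dropout step reproduces: 24/(1 − 0.20) = 30 per group, 60 in total. The 24 cannot be reproduced, because the difference to detect, the SD value and alpha are not stated. At an assumed two-sided 0.05 and 80% power, 24 per group corresponds to a difference of 0.826 SD (noncentral t, 46 df).

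**Inputs.** From the plan: n = 24 per arm. Assumed: two-sided 0.05; a difference d of 0.5 or 0.83 SD of the week-8 value; correlation ρ between baseline and week 8; share R² of outcome variance explained by age and BMI, equal at both visits; baseline SD equal to k times the week-8 SD (k = 1 unless stated).

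**Formulas.** The variance of the arm difference is 2/n times the factor below, in units of the week-8 variance. ANCOVA factors are also multiplied by 1 + q/(2n − 3 − q), the cost of chance imbalance in q covariates (1.023, 1.047 and 1.071 for q = 1, 2, 3).

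- Change contrast: 1 + k² − 2kρ, which is 2(1 − ρ) at k = 1; 46 df. Age and BMI main effects cancel.
- ANCOVA on baseline only: 1 − ρ²; 45 df.
- Week 8 with age and BMI: 1 − R²; 44 df.
- Week 8 with age, BMI and baseline: (1 − R²)(1 − r²), with r = (ρ − R²)/(1 − R²); 43 df.

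Before the small-sample cost, the change factor exceeds the baseline-only ANCOVA factor by (k − ρ)², which is never negative.

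**One case in full (d = 0.5, ρ = 0.5, k = 1).** ANCOVA: 0.75 × 1.023 = 0.767; SE = √(0.767 × 2/24) = 0.253; noncentrality 0.5/0.253 = 1.98; power 49%. Change: factor 1.00; SE = √(2/24) = 0.289; noncentrality 1.73; power 40%.

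**Baseline-only ANCOVA v change, power in %, k = 1.**

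| ρ | 0.5 SD | 0.83 SD |
|---|---|---|
| 0.5 | 49.0 v 39.6 | 89.2 v 80.0 |
| 0.6 | 55.4 v 47.5 | 93.3 v 87.9 |
| 0.7 | 65.1 v 59.1 | 97.2 v 95.1 |
| 0.8 | 79.8 v 76.5 | 99.6 v 99.3 |
| 0.9 | 97.0 v 96.6 | 100 v 100 |

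**Adding baseline to a week-8 model with age and BMI (d = 0.5, R² = 0.2).** Without baseline: 0.8 × 1.047 = 0.837, power 45.7%. With baseline at ρ = 0.5: r = 0.3/0.8 = 0.375, and 0.8 × (1 − 0.141) × 1.071 = 0.737, power 50.5%. At ρ = 0.6 and 0.7, power is 56.0 and 64.9%. If baseline carries no information after age and BMI (r = 0), power is 44.8%, a loss of about 1 point.

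**Where the proposed model can lose.** Take d = 0.5, R² = 0 and a smaller baseline SD. Age, BMI and baseline v change gives 63.0 v 65.2% (k = 0.8, ρ = 0.7), 77.8 v 80.7% (k = 0.8, ρ = 0.8) and 63.0 v 66.1% (k = 0.7, ρ = 0.7). The loss is about 2 to 3 points. With R² = 0.2 and k = 0.8, the losses at ρ = 0.7 and 0.8 shrink to 0.3 and 1.7 points.

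**Why naming the contrast matters.** A treatment main effect averaged over baseline and week 8 is not excluded by the wording. It halves the difference, with variance factor (1 + ρ)/2. At 0.826 SD its power is 41, 37 and 33% at ρ = 0.3, 0.5 and 0.7, where the one-factor ANOVA has 80%.

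**The case against.** The strongest reply has four parts.

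- **The plan may already use baseline.** Its split-plot sentence covers outcomes with repeated measures, and all of these outcomes are measured at least twice. A treatment-by-time analysis is therefore a more natural reading than a week-8 comparison that ignores baseline. This stands, and it makes the change contrast the more relevant comparator. Also, if baseline were entered as a tested term beside age and BMI (R² = 0.2), it would be kept in 73, 95 and 100% of trials at ρ = 0.5, 0.6 and 0.7. The loss against a week-8 model then arises mainly if baseline is never entered, and nothing requires entering it.
- **The gain cannot be sized from the documents.** This also stands. The 0.5 SD figures are favourable to the point. At 0.83 SD the gain over change is about 2 points at ρ = 0.7 and under 1 at 0.8.
- **Adjustment is not free in every setting.** A reader might infer that it never loses more than a trivial amount. The 2 to 3 point losses above contradict that. They need a baseline SD below the week-8 SD, which is conceivable for HbA1c because section 4.B restricts it at entry. Part of the loss is the price of age and BMI, which the plan already requires.
- **Other models are as good.** A constrained mixed model with baseline as a response is a comparable alternative. The point is to fix one model, not to insist on ANCOVA.

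**Conclusion.** The gap in pre-specification is real and clear from the text: baseline adjustment is allowed by general wording but not required, and no treatment contrast is named. Closing it is a free improvement, not the correction of an error.

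The size is conditional on assumed two-sided 0.05, ρ, k, R² and effect size. At 0.5 SD, equal SDs and ρ from 0.5 to 0.8, the gain of baseline-only ANCOVA over a change contrast is about 9 falling to 3 points. Over a week-8 model with age and BMI (R² = 0.2), it is about 5 to 19 points at ρ from 0.5 to 0.7. It is near nil over change at high ρ, and over a week-8 comparison at low ρ. The downside is about 1 point against the week-8 model and about 3 against change in the unfavourable settings shown.

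Two stronger readings are tempting. A reader might infer that the plan excludes baseline adjustment, but its wording on covariates leaves room for it. A reader might also infer that the sample size is wrong. The 30 follows from the 24, and the 24 cannot be checked from what is stated; nothing here shows either to be in error.

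**What to change.** In section 4.D, replace the rule that tests other terms for significance, and the sentence on optional covariates, with:

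> For each outcome the treatment effect is the between-group difference in least-squares means at week 8, with 95% CI, adjusted for age, baseline BMI and the baseline value of that outcome. Outcomes measured only at baseline and week 8 use ANCOVA. Outcomes also measured at week 4 use a mixed model of weeks 4 and 8 with treatment, visit, treatment-by-visit, age, baseline BMI, baseline and baseline-by-visit, with an unstructured covariance, and the week-8 contrast is the test. Covariates are fixed before any week-8 data are analysed and kept regardless of significance.

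Bring the split-plot sentence into line, so that repeated-measures analysis covers weeks 4 and 8. If the sponsor prefers a constrained mixed model with baseline as a response, that is an acceptable equivalent; state it instead.

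The deadline should be the first analysis of week-8 data, not unblinding. Section 4.A says that "investigators and subjects will not know the composition of the treatments until after the study is complete", so coded groups could be compared before the code is broken.

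The cost is wording only: no extra visit, sample or participant, and one residual degree of freedom for the baseline term in the ANCOVA. The change fixes the analysis within each outcome. It does not settle which outcome is primary.

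### Section 4.D lets significance tests on the trial data decide every model term beyond age and BMI, which mildly inflates a group-difference test; separately, no baseline-outcome covariate is named, which costs precision

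*Combined protocol and SAP*

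**What the plan says.** The analysis text is in section 4.D of the combined protocol and SAP. A mixed model is planned. On covariates it says "The model will account for age, BMI", without stating which visit's BMI is meant. It continues that "the significance for other terms will be tested to determine if they are to remain in the model", and then "Some terms may be used as covariates". There is no list of candidates, no retention level and no order of selection. The baseline value of the outcome is not named as a covariate there or elsewhere.

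On the treatment comparison it says "Split-plot and split-split plot analysis will be used to partition variances from measurements for which there are repeated measures" and "Contrasts statements or appropriate multiple comparisons of means will be completed using least-square means". Nothing states whether treatment is judged by a group main effect, a group-by-time interaction or a contrast at week 8. The sample-size paragraph points to a plain between-group comparison: "A sample size calculation was estimated for a 1-factor ANOVA for a parallel-arm study".

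Baseline values are scheduled in section 4.A: "Blood pressure will be obtained at baseline, at 4 weeks, then after 8 weeks of the study", and "Twice during the study, at baseline and after the 8-week treatment period, 25 ml of blood will be collected".

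**The concern.** A p-value assumes that the model was chosen before the data were seen. If covariates are kept because they look significant in the same data, with group already in the model, the residual variance is pulled down and the reported standard error of the group difference is too small. The false-positive rate then depends on how many terms are tried and how prognostic they are. The plan limits neither.

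The baseline outcome raises a different issue. It is usually among the strongest predictors of the week-8 value, yet under this text it enters as a covariate only if the analyst proposes it and it passes the test. What is lost there is power, not error control.

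**Working it through.** **Inputs.** From section 4.D: 24 completers and 30 recruited per group, 20% dropout, power above 80%, age and BMI always kept. Assumed, because the documents give none: two-sided 5% level, number and strength of candidates, retention level, baseline-to-week-8 correlation ρ.

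**1. The plan's own figure.** 24/(1 − 0.20) = 30, so the dropout step reproduces. The 24 cannot be checked, because the SD, target difference, level and sidedness are not stated. At two-sided 5% and 80% power it implies a standardised difference of (1.960 + 0.842) × √(2/24) = 2.802 × 0.2887 = 0.81, used in step 4.

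**2. Selection with group in the model.** Simulation with no true effect and 24 per group. Group, age and BMI are forced in, candidates are removed backward at p > 0.05, and group is then tested as if the model had been fixed. With 20,000 replicates per cell, the Monte Carlo error near 5% is √(0.05 × 0.95/20,000) = 0.15 points.

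| Candidates | Pure noise | Each explains 2% of variance | Each explains 5% |
|---|---|---|---|
| 3 | 5.3% | 5.6% | 6.3% |
| 5 | 5.5% | 6.1% | 7.3% |
| 10 | 6.7% | 7.8% | 10.1% |

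Fixed models (age and BMI only, or with all candidates) gave 4.7-5.4%. Retention levels of 0.10 and 0.20 gave 5.4-6.1%, 6.1-7.0% and 7.4-9.5% for 3, 5 and 10 candidates. The largest cell in the table needs 10 × 5% = 50% of the variance explained.

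The cause shows in the standard errors at 5% of variance each. With 5 candidates the mean reported value is 0.264 against an actual SD of 0.292 (ratio 0.90). With 10 it is 0.228 against 0.277 (ratio 0.82).

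**3. Where there is no inflation.**
- Group-by-time contrast, two visits, complete data: 4.6-5.4%. Subject-level main effects cancel out of the within-subject change, so selecting them has no effect.
- Selection without group in the model: 4.7-5.2%. With no true effect, randomised group is independent of outcome and candidates, so a selection that never sees group cannot favour a group difference.

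**4. Leaving out baseline.** Fixed age and BMI without baseline gave 4.8-5.2%, so the error rate holds. For precision, with equal variances at both visits, the variance of the adjusted estimate relative to the week-8 comparison is 1 − ρ². Relative to the change comparison it is (1 − ρ²)/[2(1 − ρ)] = (1 + ρ)/2. Power at a standardised difference of 0.81, 24 per group:

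| ρ (assumed) | Week 8 only | Change | Baseline-adjusted |
|---|---|---|---|
| 0.3 | 80% | 66% | 84% |
| 0.5 | 80% | 80% | 90% |
| 0.6 | 80% | 88% | 94% |
| 0.7 | 80% | 95% | 98% |

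**The case against.** The strongest reply is that the plan names a split-plot mixed model and schedules its outcomes at baseline and week 8, so group-by-time is the natural treatment test. That test is not inflated by selecting subject-level terms, and baseline is then used as a repeated response rather than ignored. This stands, and it makes the first point conditional. It does not remove it: section 4.D never names the contrast, and the least-square-means comparisons and the 1-factor ANOVA fit a group difference equally well. Nor does it answer the second point, since with two visits the group-by-time contrast is the comparison of change, the less precise middle column in step 4.

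It can also be said that the inflation is small and rests on assumed inputs. That stands too. With 3 noise candidates, 5.3% lies inside the fixed-model range of 4.7-5.4%.

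Blinding might be thought to keep group out of the selection. Section 4.A conceals what the treatments contain; it does not say that terms are chosen without group in the model.

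A reader might go further and infer that group-by-time is itself a term to be tested and dropped, with the group main effect then tested, so that the chance of either being significant is 1 − 0.95² = 9.75%. The documents do not support resting the point on that. Only age and BMI are exempted by name, but the same literal reading would let treatment be dropped as well, which cannot be meant. That figure also describes two tests being tried, not an understated standard error.

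**Conclusion.** Both points hold, at minor to moderate size.

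1. If treatment is tested as a group difference and terms are selected with group in the model, type I error is about 5-6% with 3 candidates, 5.5-7% with 5 and 7-10% with 10. This assumes a two-sided 5% level, 24 per group and a retention level of 0.05. No single figure can be given, and 10% should not be quoted as the expected rate.
2. Not naming the baseline outcome costs precision when treatment is tested at week 8 or as change. A reader might infer that it also inflates type I error, or that baseline goes unused. Neither follows: fixed models without it hold about 5%, and a split-plot analysis can carry baseline as a response.

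**What to change.** Delete the clause "the significance for other terms will be tested to determine if they are to remain in the model" and the sentence "Some terms may be used as covariates". For each outcome, fit one fixed model for the between-group difference at week 8, with the baseline value of that outcome, age and baseline BMI kept whatever their p-values. Label any model with further terms as exploratory.

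If a repeated-measures model is preferred for the outcomes with a week-4 visit, name it in advance as the single main analysis. Always keep group-by-time, let the age and BMI effects differ by visit, and use REML with a small-sample degrees-of-freedom correction. Do not describe it as interchangeable with the baseline-adjusted model. In simulation, entering age and BMI as plain main effects moved the treatment estimate by up to 0.16 SD, and even the matching version had maximum-likelihood standard errors about 6% smaller. Offering both would leave a choice open to the analyst.

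The cost is small: the measurements are already scheduled and only the analysis text changes. The downside is that a strong unlisted predictor could not be added to the main analysis later. One explaining 10% or 20% of residual variance would have multiplied the standard error by √0.90 = 0.949 or √0.80 = 0.894, so about 5% or 11% is forgone.

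### If correlation between visits decays with time, the split-plot error understates the standard error of the week-8-minus-baseline arm contrast for outcomes measured at three visits

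*Combined protocol and SAP*

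**What the plan says.** The analysis paragraph of section 4.D opens with a mixed model: "The data will be analyzed using a mixed model in order to partition variance from random and fixed effects". For repeated measures it then names the method: "Split-plot and split-split plot analysis will be used to partition variances from measurements for which there are repeated measures". Treatment comparisons follow from the fitted means: "Contrasts statements or appropriate multiple comparisons of means will be completed using least-square means". On covariates it says "The model will account for age, BMI and the significance for other terms will be tested"; the baseline value of the outcome is not among those named. The paragraph gives no covariance structure, sphericity correction, degrees-of-freedom method, alpha, primary contrast or primary time point.

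Section 4.A sets the visits. For blood pressure, "Blood pressure will be obtained at baseline, at 4 weeks, then after 8 weeks of the study", and within a visit "Blood pressure will be measured three times with a Dinamap Compact Blood Pressure Monitor". For the body measurements, "Body weight and composition, and waist/hip circumference will be obtained at baseline, at 4 weeks, then after 8 weeks of the study". Blood is different: "Twice during the study, at baseline and after the 8-week treatment period, 25 ml of blood will be collected". Urine is also collected only at baseline and after 8 weeks.

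**The concern.** A split-plot analysis has two error terms: one between men, and one pooled within men. In a field trial the sub-plot treatments are randomised within the whole plot, which justifies a single pooled error. Visits cannot be randomised in time. The pooled within-man error is right for every pair of visits only if variances are equal and the three correlations (baseline with week 4, week 4 with week 8, baseline with week 8) are the same.

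Measurements far apart in time are often less alike than measurements close together. The change from baseline to week 8 then varies more than the pooled error says, and the change from baseline to week 4 varies less. The end-of-treatment comparison would get confidence intervals that are too narrow and p-values that are too small. This matters most for blood pressure, the only outcome that the sample-size paragraph mentions. Change from baseline is a natural contrast here, because baseline is one of the repeated visits and is not listed as a covariate.

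**Working it through.** **The plan's own figure.** The documents state no type I error rate. The only figure that can be reproduced is the dropout inflation, 24/(1 − 0.20) = 30 per group. The 24 cannot be checked, because no difference, standard deviation or alpha is given. It does not affect this point except as the number of men per arm.

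**Inputs.** From the documents: two arms, 24 evaluable men per arm, visits at weeks 0, 4 and 8. Assumed: two-sided 5%, unit variance at each visit (except where stated), complete data, and the correlations below.

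**Formulae.** Let r04, r48 and r08 be the correlations between visits.

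- True variance of one man's week-8-minus-baseline change: 2(1 − r08).
- Variance that the pooled split-plot error implies for any pair of visits: 2(1 − r̄), with r̄ = (r04 + r48 + r08)/3.
- Ratio k = (1 − r08)/(1 − r̄). The split-plot standard error is 1/√k of the true one.
- Actual type I error ≈ 2[1 − Φ(1.96/√k)].

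Under AR(1) with adjacent correlation ρ, k = 3(1 + ρ)/(3 + ρ) for week 8 minus baseline, and k = 3/(3 + ρ) for week 4 minus baseline.

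**One case in full, ρ = 0.7.** r08 = 0.49 and r̄ = (0.7 + 0.7 + 0.49)/3 = 0.63. True variance is 2 × 0.51 = 1.02; pooled variance is 2 × 0.37 = 0.74. k = 1.02/0.74 = 1.378 and √k = 1.174. Type I error is 2[1 − Φ(1.96/1.174)] = 2[1 − Φ(1.67)] = 9.5%.

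**Week 8 minus baseline** (simulation: 24 per arm, 20,000 trials per setting):

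| Correlation pattern | k | SE too small by | Type I, formula | Type I, simulation |
|---|---|---|---|---|
| Equal (0.6 throughout) | 1.000 | 0% | 5.0% | 5.0% |
| 0.65 adjacent, 0.60 for weeks 0–8 | 1.091 | 4% | 6.1% | 6.0% |
| AR(1) 0.3 | 1.182 | 8% | 7.1% | 7.3% |
| AR(1) 0.5 | 1.286 | 12% | 8.4% | 8.3% |
| AR(1) 0.7 | 1.378 | 15% | 9.5% | 9.6% |
| AR(1) 0.8 | 1.421 | 16% | 10.0% | 10.0% |

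A stable man effect plus AR(1) plus noise, with variance shares 0.5/0.25/0.25 and ρ = 0.7, is another mild case. It gives r04 = r48 = 0.5 + 0.25 × 0.7 = 0.675, r08 = 0.5 + 0.25 × 0.49 = 0.6225, k = 0.3775/0.3425 = 1.102, and 6.2%. A pattern slightly less mild (r04 0.65, r08 0.60, r48 0.70) gives k = 0.40/0.35 = 1.143 and 6.7%.

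**Other contrasts from the same split-plot model.**

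- Week 4 minus baseline, AR(1): k = 3/3.3 = 0.909 at ρ = 0.3, giving 4.0%; k = 3/3.8 = 0.789 at ρ = 0.8, giving 2.7%. This contrast is conservative.
- Plain week-8 difference in least-square means: its variance combines both error terms and estimates the average of the visit variances. With equal variances that is correct whatever the correlations, and simulation gives 4.8 to 5.2%. If the week-8 standard deviation were 15% larger, simulation gives 7.4%, but that comes from unequal variance, not unequal correlation.
- Baseline as covariate, with weeks 4 and 8 as the repeated visits, AR(1): k = 2(1 + ρ²)/(2 + ρ²), giving 5.5% at 0.3, 6.3% at 0.5 and 7.9% at 0.8.

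**With the contrast's own variance**, as an unstructured covariance supplies, week 8 minus baseline runs at 4.7 to 5.3% in every setting simulated. Week-8 analysis of covariance on baseline alone gives 4.7 to 5.2%.

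**The case against.** The strongest reply is that section 4.D says mixed model and never states compound symmetry; split-plot may only describe the layers, man and visit. This stands in part. The covariance is not spelled out, so one cannot be certain what will be fitted. But split-plot is the only repeated-measures method named, and nothing in the paragraph relaxes its pooled error. On the looser reading the covariance is simply not specified, and the same edit settles both.

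The second reply is that the size depends on assumed correlations. This stands. Pure AR(1) has no stable man effect and no measurement noise, so its upper values are strong assumptions for blood pressure; the milder patterns give 6 to 6.5%. If baseline and week 8 were more alike than adjacent visits (0.6 against 0.5), the test would be conservative, at 3.4% by the formula and 3.6% by simulation. That ordering is hard to defend for these outcomes, but the documents do not rule it out.

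A reader might infer that every week-8 comparison in this trial runs at 7 to 10%. The documents do not support that. The contrast wording in section 4.D also allows the plain week-8 difference in means, which holds its level if variances are equal, and blood and urine outcomes have only one pair of visits.

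A reader might also infer that a split-split level for the three blood pressure readings adds a further error. The plan does not say that the readings form that level. If they do, in balanced data the arm-by-visit contrast is tested against the visit-within-man error, exactly as if the readings had been averaged.

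**Conclusion.** The point holds for one contrast under one condition. For blood pressure, weight, body composition and waist/hip, a split-plot error pooled over three visits understates the standard error of the week-8-minus-baseline arm contrast if correlation decays with time. At a nominal two-sided 5%, type I error is then about 6 to 6.5% with mild decay and 7 to 10% under AR(1) 0.3 to 0.8. With equal variances and equal correlations there is no inflation. The result rests on the literal reading of split-plot, an assumed alpha, equal visit variances, complete data and assumed correlations. It is worth correcting before the data are analysed: the contrast is a natural one for the outcome that the sample-size paragraph mentions, and the remedy costs almost nothing.

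**What to change.** In section 4.D, for outcomes measured at three visits, replace the split-plot error with a mixed model that has an unstructured covariance across visits and Kenward-Roger degrees of freedom. State that the treatment comparison is the week-8 arm contrast, either as change from baseline or adjusted for baseline, and give its alpha and sidedness. Week-8 analysis of covariance on baseline alone also holds its level and is a simpler alternative. Averaging the three blood pressure readings to one value per visit is an optional simplification, not a correction.

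The cost is one rewritten sentence and a covariance option in the software. Three visits need 6 covariance parameters (3 variances and 3 correlations), which 48 to 60 men can support. If correlations really are equal, the error degrees of freedom fall from 92 (2 × 46) to 46 (2 × 23), and the critical t rises from 1.99 to 2.01, so intervals widen by about 1% (2.01/1.99 = 1.01).
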